Official title: Evaluation of the clinical and molecular efficacy of daily avanafil in Egyptian males with erectile and endothelial dysfunction (Randomized Placebo-Controlled study)

NCT number: NCT04374994

Document date: 20-9-2018

INTRODUCTION

Penile erection is a neurovascular process that occurs in response to the activation of pro-erectile autonomic pathways and is controlled by numerous tightly regulated events. Pathologic alteration in the endothelium of penile vasculature and/or erectile tissue and/or impairment of neurovascular processes can result in erectile dysfunction (ED).⁽¹⁾

Erectile dysfunction, the persistent inability to achieve or maintain an erection for satisfactory sexual performance, is a highly prevalent disorder associated with a significant burden of illness. The prevalence and incidence of ED are strongly age-related, affecting more than half of men >60 years.⁽²⁻⁴⁾

Erectile dysfunction is an early symptom or alert of cardiovascular disease, due to the common risk factors and pathophysiology mediated through endothelial dysfunction that may explain the association between ED and other vascular disease e.g., DM, CVD, and atherosclerosis.⁽⁴⁾

The vascular endothelium is involved in numerous physiologic functions and its dysfunction leads to impaired vasodilatation. This is attributed to decreased bioavailability of nitric oxide (NO) which is a molecule with a key role in vascular tone regulation and thus impaired NO bioactivity is a major pathogenic mechanism of ED.^(5,6)

Endothelin-1 (ET-1) is a 31-amino-acid peptide with potent and prolonged vasoconstrictor activity. It exerts its biological effect through the activation of specific endothelin receptors. Endothelin receptors have been found in human corporal smooth muscle membranes. ED was suggested to be

the result of impaired endothelium-dependent smooth muscle relaxation due to increased release of ET-1. ^(7,8)

Oral phosphodiesterase type 5 (PDE5) inhibitors are recommended as first-line therapy for ED of varying aetiology and severity. ^(9,10)

However, many patients are dissatisfied with available therapies due to high cost, adverse events and perceived lack of efficacy. Therefore, the development of novel PDE5 inhibitors with enhanced selectivity, faster onset of action, increased potency and improved tolerability is desirable. ^(11,12)

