Recently, a new PDE5i, avanafil, has become available worldwide. The evaluation of safety profile suggests that avanafil is associated with a lower incidence of side effects and approved for the treatment of ED by both the US Food and Drug Administration (FDA) and the European Medicines Agency (EMA) in April 2012 and in June 2013, respectively. ⁽¹³⁻¹⁵⁾

The most important characteristic of avanafil, in comparison to the first-generation PDE5is, is its high selectivity for PDE5, particularly in relation to PDE6, PDE1, and PDE11. Avanafil has selectivity for PDE5 over PDE1 and PDE6 similar to tadalafil, but, unlike tadalafil, has negligible affinity for PDE11. ^(14,15)

AIM OF THE WORK

The aim of the work is to investigate the impact of daily avanafil on the function and levels of some soluble molecular markers of penile endothelium in men with erectile dysfunction.

PATIENTS

The study will be conducted on 140 adult males complaining of ED associated with diseases that may affect endothelial function such as diabetes mellitus, hypertension and/or dyslipidemia from outpatient clinic of Dermatology, Venereology and Andrology Department of the Alexandria main University Hospital.

They will be randomized into two groups:

Intervention group: will include seventy adult males and will receive daily avanafil for four weeks.

Control group: will include seventy adult males and will receive a placebo instead.

- An informed consent will be taken from all subjects prior to the onset of the study.
- Approval of the medical ethics committee of Alexandria Faculty of Medicine will be obtained.

Exclusion criteria:

1. Patients aged < 18 years.
2. Patients with contraindications to treatment by PDE inhibitors.
3. Patients with diseases that increase the risk of priapism (eg, leukemia and multiple myeloma).

METHODS

ALL studied groups will be subjected to:

1. Full history taking with complete general and genital examination.
2. Diagnosis and severity of ED was determined according to IIEF-5 questionnaire. Erectile dysfunction will be defined as a score of < 22 in the self reported International Index of Erectile Function-5 questionnaire (IIEF-5).⁽¹⁶⁾

The International Index of Erectile Function (IIEF-5) Questionnaire

Over the past 6 months:					
1. How do you rate your confidence that you could get and keep an erection?	Very low 1	Low 2	Moderate 3	High 4	Very high 5

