2. When you had erections with sexual stimulation, how often were your erections hard enough for penetration?	Almost never/never 1	A few times (much less than half the time) 2	Sometimes (about half the time) 3	Most times (much more than half the time) 4	Almost always/always 5
3. During sexual intercourse, how often were you able	Almost never/never 1	A few times (much	Sometimes (about half the time) 3	Most times (much	Almost always/always 5

The International Index of Erectile Function (IIEF-5) Questionnaire

to maintain your erection after you had penetrated (entered) your partner?		less than half the time) 2		more than half the time)4	
4. During sexual intercourse, how difficult was it to maintain your erection to completion of intercourse?	Extremely difficult 1	Very difficult 2	Difficult 3	Slightly difficult 4	Not difficult 5
5. When you attempted sexual intercourse, how often was it satisfactory for you?	Almost never/never 1	A few times (much less than half the time) 2	Sometimes (about half the time) 3	Most times (much more than half the time) 4	Almost always/always 5

IIEF-5 scoring:

The IIEF-5 score is the sum of the ordinal responses to the 5 items.

22-25: No erectile dysfunction

17-21: Mild erectile dysfunction

The International Index of Erectile Function (IIEF-5) Questionnaire

12-16: Mild to moderate erectile dysfunction

8-11: Moderate erectile dysfunction

5-7: Severe erectile dysfunction

3. The patients in the intervention group will receive avanafil 50 mg orally for 4 weeks. They will be instructed to take their medication on an empty stomach every evening. A total of 28 pills will be prescribed at study entry and patients will be asked to count and report any unused medication at the end-of-study visit.
4. The patients in the control group will receive placebo tablets for 4 weeks.
5. Markers of endothelial function will be measured in plasma at baseline and end of treatment using standard methods and commercially available kits (Human Endothelin 1(ET-1) ELISA Kit, Nitric oxide (NO) ELISA Kit and Human Cyclic guanosine monophosphate(cGMP) ELISA Kit).⁽¹⁷⁻¹⁹⁾
6. The primary outcome will be the percentage of change of NO, cGMP and ET1 serum levels from baseline to 4 weeks posttreatment with avanafil.
7. The secondary outcome will be comparing avanafil with placebo group regarding posttreatment NO, cGMP and ET1 serum levels and percentage of change from baseline.

ETHICS OF RESEARCH

Research on human or human products:

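### cGMP is labelled a primary marker of endothelial function, but under a PDE5 inhibitor the design cannot separate reduced cGMP breakdown from increased NO-driven production

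*Protocol*

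**What the plan says.** The stated aim is to "investigate the impact of daily avanafil on the function and levels of some soluble molecular markers of penile endothelium". METHODS item 5 puts this into practice: "Markers of endothelial function will be measured in plasma at baseline and end of treatment". The kits named there are for endothelin-1, plus "Nitric oxide (NO) ELISA Kit and Human Cyclic guanosine monophosphate(cGMP) ELISA Kit". Item 6 then says "The primary outcome will be the percentage of change of NO, cGMP and ET1 serum levels from baseline to 4 weeks posttreatment with avanafil". Item 7 makes the comparison with placebo, on the same three analytes, the secondary outcome.

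The Introduction gives an endothelial rationale for two of the three. For NO it describes decreased bioavailability and says that "impaired NO bioactivity is a major pathogenic mechanism of ED". For ET-1 it describes increased release that impairs endothelium-dependent relaxation. It gives no such rationale for cGMP. Of the drug, the Introduction says "The most important characteristic of avanafil, in comparison to the first-generation PDE5is, is its high selectivity for PDE5".

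The SAP lists paired and two-group tests at the 5% level. Neither document says how to interpret a rise in cGMP when NO and ET-1 do not change.

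**The concern.** The three analytes carry one label and equal primary status, yet they stand in different relations to the drug. Avanafil blocks the enzyme that breaks down cGMP. NO and ET-1 are not substrates of that enzyme. cGMP could therefore rise on treatment because it is cleared more slowly, with no change in what the endothelium produces.

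What is at stake is the wording of the conclusion. If cGMP rises while NO and ET-1 stay flat, the item 5 label allows this to be reported as a primary finding on endothelial function. The data would be equally compatible with the ordinary pharmacology of the drug class.

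**Working it through.** The plan has no figure on this point to reproduce. It gives 140 men, 70 per arm, and a 5% significance level, but no effect size, standard deviation or power. The check is mainly one of reasoning, followed by an illustration on stated assumptions.

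**Step 1: what the documents supply.**
- cGMP is grouped as an endothelial marker (METHODS item 5) and is primary (item 6).
- The drug is a selective PDE5 inhibitor (Introduction).
- Dosing is every evening for 4 weeks (METHODS item 3; PATIENTS).
- The second sample is at end of treatment in item 5, but at four weeks posttreatment in item 6, which could also be read as after stopping.
- The interval from last dose to blood draw is not stated. No off-drug sample and no functional endothelial test is planned.

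The documents do not say in words that PDE5 breaks down cGMP. This follows from the drug class they name.

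**Step 2: can the design tell the explanations apart?** Take a simple steady state, level = production / clearance. Three different situations give the same 25% rise:
- clearance cut by 20%, production unchanged: 1 / 0.80 = 1.25
- production up 25%, clearance unchanged: 1.25 / 1 = 1.25
- production up 12.5%, clearance cut by 10%: 1.125 / 0.90 = 1.25

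The within-arm change in item 6 is the same in all three. So is the avanafil-placebo difference in item 7, because only the avanafil arm has PDE5 inhibited. Randomisation supports the statement that avanafil raised cGMP, but does not say by which route.

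**Step 3: could slower breakdown alone give a significant result?** Assumptions, none from the documents: production unchanged, no mean change on placebo, equal SD of percentage change in both arms, all 70 per arm analysed, two-sided 5%, normal approximation.
- Rise from a fractional clearance cut x: x / (1 − x). For x = 0.10 this is 0.10 / 0.90 = 11.1%. For x = 0.20 it is 0.20 / 0.80 = 25.0%.
- Power ≈ Φ(rise / (SD × √(2/70)) − 1.96).
- Example, x = 0.20 and SD 40 points: 40 × √(2/70) = 6.76; 25.0 / 6.76 = 3.70; 3.70 − 1.96 = 1.74; Φ(1.74) = 0.96.

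| Clearance cut | cGMP rise | SD 20 | SD 40 | SD 60 | SD 80 |
|---|---|---|---|---|---|
| 10% | 11.1% | 91% | 38% | 19% | 13% |
| 20% | 25.0% | ~100% | 96% | 69% | 46% |

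So a significant cGMP difference with no endothelial change is possible over a wide range of assumptions. The table shows possibility, not likelihood.

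**The case against.** The strongest reply has four parts.

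- **The pharmacological premise is incomplete.** The protocol speaks of selectivity among isoenzymes and never says that plasma cGMP will move at this dose and sampling time. This stands as a limit: the size of any direct effect is unknown. The drug class is still enough to make slower breakdown a live explanation.
- **cGMP lies downstream of NO, so it is reasonable to measure it.** This stands. A reader might infer that a cGMP rise shows only that the drug is present and can say nothing about the endothelium. The documents do not support that, because a rise may include greater NO-driven production. The defensible statement is that the two routes cannot be separated.
- **No success rule exists.** There is no composite, weighting or any-of-three criterion, and a reader shown all three results would see the discordance. This also stands. A reader might infer that the plan would declare endothelial benefit on cGMP alone, but no passage says so. The risk comes from the item 5 label, the primary status and the aim, with no rule to prevent that reading.
- **The title names molecular efficacy as the object of study, and cGMP levels answer that directly.** This is fair. It leaves cGMP useful as a molecular outcome but does not justify the endothelial label.

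It is also tempting to say that a third of the primary outcome is invalid. One marker in three is a count, not a size of bias, and the point does not apply to NO or ET-1.

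**Conclusion.** The concern holds as a matter of labelling and interpretation. As planned, a higher end-of-treatment cGMP on avanafil may reflect reduced breakdown, increased NO-driven production, or both, and neither planned comparison separates them. How far reduced breakdown contributes depends on how much drug is acting at sampling. That is unknown, because the dose-to-sample interval is unstated and items 5 and 6 describe the sampling time differently.

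The documents support no estimate of magnitude. The conclusion rests on the drug class named in the protocol and on reading item 5 as sampling under, or shortly after, daily dosing. It does not invalidate the cGMP measurement or the primary outcome as a whole. It limits what a cGMP result may be said to show.

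**What to change.** 1. In METHODS items 5 to 7, keep measuring cGMP but label it a pharmacodynamic marker of the NO-cGMP pathway. Keep NO and ET-1 as the endothelial markers.
2. State that an effect on endothelial function will be concluded only from the randomised avanafil-placebo difference in NO and ET-1. At present that comparison is only the secondary outcome.
3. Fix the rule in advance, choosing one of two: both differences significant at 5%; or either one after a Holm correction across the two (smaller p-value against 0.05 / 2 = 0.025, then the larger against 0.05). Without a correction, an either-one rule on two independent tests has a false-positive chance of 1 − 0.95² = 9.75%.
4. State that a change in cGMP without a change in NO or ET-1 will be reported as consistent with PDE5 inhibition, and not as evidence of improved endothelial function.
5. Reconcile the sampling time in item 5 with that in item 6, and record for each man the time from last dose to blood draw.

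No new assay or visit is needed and the sample size stays the same. The cost is revised wording, one extra recorded time per man, and the loss of the option to present a cGMP-only result as endothelial benefit.

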Official title: Evaluation of the clinical and molecular efficacy of daily avanafil in Egyptian males with erectile and endothelial dysfunction (Randomized Placebo-Controlled study)

NCT number: NCT04374994

Document date: 20-9-2018

Statistical analysis of the data: Data were fed to the computer and analyzed using IBM SPSS software package version 20.0. Qualitative data were described using number and percent. Quantitative data were described using range (minimum and maximum), mean, standard deviation and median. Significance of the obtained results was judged at the 5% level. Student t-test was used for normally distributed quantitative variables, to compare between two studied groups. Mann Whitney test for abnormally distributed quantitative variables, to compare between two studied groups. Wilcoxon signed ranks test, for abnormally distributed quantitative variables, to compare between two periods. Paired t-test for normally quantitative variables, to compare between two periods Spearman coefficient for correlation between two abnormally quantitative variables.

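### The primary outcome is the before-after change on avanafil; the randomised comparison with placebo is only secondary

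*Protocol*

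**What the plan says.** The protocol's title describes a randomised, placebo-controlled trial. Under PATIENTS, "The study will be conducted on 140 adult males complaining of ED", and "They will be randomized into two groups" of seventy each; the second is described as "Control group: will include seventy adult males and will receive a placebo instead". Under AIM OF THE WORK, the purpose is to "investigate the impact of daily avanafil on the function and levels of some soluble molecular markers".

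The outcomes are in METHODS:

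- Item 6: "The primary outcome will be the percentage of change of NO, cGMP and ET1 serum levels from baseline to 4 weeks posttreatment with avanafil".
- Item 7: "The secondary outcome will be comparing avanafil with placebo group regarding posttreatment NO, cGMP and ET1 serum levels and percentage of change from baseline".

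The SAP's single paragraph lists tests by data type. For two groups, "Student t-test was used for normally distributed quantitative variables, to compare between two studied groups", with Mann-Whitney for non-normal data. For two time points it has the paired t-test and "Wilcoxon signed ranks test, for abnormally distributed quantitative variables, to compare between two periods". It does not say which test serves the primary outcome and which the secondary.

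**The concern.** The aim is causal: what avanafil does to the markers. In this design only the difference between the randomised arms answers that. A before-after change in the treated arm mixes any drug effect with everything else that moves a marker over four weeks, such as a time trend, assay drift between runs, or other care for diabetes, hypertension or dyslipidaemia. The placebo arm is there to remove those influences, and the primary outcome as worded does not use it.

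The practical risk is a trial that reports a positive primary result while avanafil and placebo do not differ, with the comparison that would reveal this given only secondary weight.

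**Working it through.** **Step 1. What do items 6 and 7 mean together?** Item 6 ends by tying the change to avanafil and mentions neither placebo nor a difference. Item 7 assigns the between-arm comparison of post-treatment levels and of percentage change to the secondary outcome. If item 6 were also a between-arm comparison of percentage change, the same analysis would be both primary and secondary. The reading that gives each item its own content is that item 6 is the within-avanafil change and item 7 the randomised comparison. The SAP's paired tests fit item 6 so read, and nothing in the SAP reverses the ranking.

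**Step 2. How often would the primary result mislead?** The documents give no SD, expected change or power, so there is no planned figure to reproduce. What follows is an illustration.

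- From the documents: 70 per arm (PATIENTS); 5% significance level (SAP).
- Assumed: two-sided testing, complete follow-up, one marker, normally distributed levels, no drug effect, and the same shift d in both arms, in SDs of the change score.

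For the paired t-test in the avanafil arm, the rejection rate is the probability that a noncentral t with 69 df and noncentrality d × √70 falls beyond the two-sided 5% limits. At d = 0.20, for example, the noncentrality is 0.20 × √70 = 1.67 and the rate is 0.378. The between-arm column is the simulated rejection rate of an ANCOVA on the week-4 level adjusted for baseline (20,000 runs per cell; baseline to week-4 correlation r = 0.3, 0.5 and 0.7).

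| Common shift d (SD of change) | Paired test, avanafil arm only | Between-arm ANCOVA |
|---|---|---|
| 0 | 5% | about 5% |
| 0.20 | 37.8% | about 5% |
| 0.25 | 54.1% | about 5% |
| 0.34 | 80.1% | about 5% |

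Over all shifts and correlations the simulated ANCOVA rate was 4.8% to 5.3%. A between-arm t-test on change also held its level, at 4.8% to 5.2%.

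**Step 3. Does percentage change alter the picture?** Step 2 uses absolute change, whereas item 6 specifies percentage change. A one-sample test of mean percentage change is biased upward even with no shift, because the ratio of two noisy positive values averages above 1. With assumed lognormal levels, log-scale SD 0.1 to 0.5, r = 0.5 and n = 70, it rejects about 7% to 44% of the time at zero shift, while the between-arm test on percentage change stays near 5%. For that test, the 5% in the table's first row is therefore a favourable figure.

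**Step 4. What does the randomised comparison cost in sensitivity?** Detectable effects at 80% power, in SD of the marker level:

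- Paired test: 0.340 × √(2(1 − r)).
- ANCOVA, 70 per arm, 137 df: the unadjusted two-sample value × √(1 − r²). The unadjusted value is 0.477 at 5% and 0.553 at 5%/3 = 1.67%.

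| Assumed r | Paired, 5% | ANCOVA, 5% | ANCOVA, 1.67% |
|---|---|---|---|
| 0.3 | 0.402 | 0.455 | 0.527 |
| 0.5 | 0.340 | 0.413 | 0.479 |
| 0.7 | 0.263 | 0.341 | 0.395 |

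At r = 0.5, for example, 0.477 × √(1 − 0.25) = 0.413.

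**The case against.** Item 6 never says within-group. It names a variable and a time point but no test, null hypothesis or decision rule, and it sits in a list that applies to all studied groups in a trial whose title calls it placebo-controlled. It could be a loosely drafted between-arm outcome. That is possible but less natural: items 3 and 4 of the same list are also specific to one arm, and the between-arm reading makes item 6 repeat part of item 7. Even on that reading, the primary comparison is unstated and the wording has to change.

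Second, the randomised comparison is planned on the same markers, both arms are measured, and the SAP contains between-group tests. This stands. The trial is not uncontrolled and no data are lost; the defect is in which result is primary.

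Third, the shift sizes are assumptions and the main illustration uses absolute change. Both are true. With no shift the paired test on absolute change keeps its 5%, so the harm there depends on some common movement. The plan gives no ground for ruling one out, and moving to percentage change makes the within-arm test worse.

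Fourth, correcting the ranking does not strictly require ANCOVA or a multiplicity rule; a between-arm t-test on change would also hold the error rate. This is fair. ANCOVA is preferred for efficiency, and sharing the 5% level among three markers is a separate matter that has to be settled once three between-arm comparisons become primary.

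**Conclusion.** The concern holds. As written, the primary outcome is a before-after change in the avanafil arm and the randomised comparison is secondary, which does not match the stated aim. This must be fixed, because the primary outcome determines the headline claim. The conclusion rests on reading items 6 and 7 together and on the SAP's silence; it does not depend on any numerical assumption. The rates of 38%, 54% and 80% show how far a modest common shift could mislead. They are not estimates of what will happen in this trial.

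**What to change.** In the protocol, make the primary outcome the avanafil-versus-placebo difference in the week-4 level of NO, cGMP and ET-1, each adjusted for its own baseline value, in all randomised patients by assigned arm. In the SAP, name the test: ANCOVA with arm and baseline level, on the log scale if the data are skewed, with the scale chosen on pooled data without arm labels. State how the three markers share the 5% level, for example Holm at two-sided 5% overall. Report within-arm changes and percentage changes as descriptive only, with no efficacy claim.

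Patients, samples and visits are unchanged. The cost is sensitivity. At r = 0.5, the detectable effect rises from 0.34 SD (paired) to 0.41 SD (ANCOVA, one marker at 5%). The further rise to 0.48 SD at the strictest Holm step is the price of multiplicity control, not of changing the ranking.

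The SAP is written in the past tense, although it carries the same date as the protocol. If any analysis had already been done when the change is made, the new primary outcome must be disclosed as post hoc.

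### The only named comparison with placebo has two metrics per marker, no regression adjustment for baseline and no rule for which decides; one pre-specified ANCOVA per marker would settle this and usually be more precise

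*Protocol*

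**What the plan says.** METHODS item 7 of the protocol (secondary outcome) plans "comparing avanafil with placebo group regarding posttreatment NO, cGMP and ET1 serum levels and percentage of change from baseline". This is the only outcome whose wording sets avanafil against placebo.

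Item 6 reads: "The primary outcome will be the percentage of change of NO, cGMP and ET1 serum levels from baseline to 4 weeks posttreatment with avanafil". It makes percentage change the primary metric but does not mention the placebo arm.

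Item 5 provides the baseline data: "Markers of endothelial function will be measured in plasma at baseline and end of treatment". The PATIENTS section puts 70 men in each arm; for the comparator, "Control group: will include seventy adult males and will receive a placebo instead".

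For two groups the SAP names two tests: "Student t-test was used for normally distributed quantitative variables, to compare between two studied groups" and "Mann Whitney test for abnormally distributed quantitative variables, to compare between two studied groups". For two time points it names two more: "Wilcoxon signed ranks test, for abnormally distributed quantitative variables, to compare between two periods" and "Paired t-test for normally quantitative variables, to compare between two periods". It contains no model with a covariate, no ranking of the two item 7 metrics, and no between-arm estimate with a confidence interval.

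**The concern.** Item 7 is the only place where the plan uses the randomisation, so any claim that avanafil changes NO, cGMP or ET-1 relative to placebo rests on it. Two things are unsatisfactory.

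- **The deciding result is not defined.** Post-treatment level and percentage change can give different answers for the same marker. Item 6 prefers percentage change, but for an outcome with no placebo comparison in its wording, so the choice in item 7 stays open. If a significant result on either metric were taken as an effect, the false-positive risk per marker would exceed 5%. The plan does not state such a rule, but nothing in it rules one out.
- **Baseline is used poorly or not at all.** A test on post-treatment level ignores baseline. Percentage change uses it only as a divisor, which is not regression adjustment and adds noise when baseline and week 4 are weakly correlated. The paired tests use baseline but do not compare arms.

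**Working it through.** **Inputs from the documents:** 70 per arm, 140 in total; 5% significance level; three markers measured at baseline and end of treatment. There is no power statement to reproduce.

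**Assumed, because the documents are silent:** two-sided testing, no dropout, baseline to week-4 correlation r = 0.3 to 0.7, coefficient of variation (CV) 30-50%, normal or lognormal markers. The reference effect is the one an unadjusted t-test detects with 80% power: sqrt(2/70) × (1.960 + 0.842) = 0.474 SD.

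**Step 1: closed form, one scale, equal SDs.** Relative to the post-treatment comparison, the variance is 1 for post level, 2(1 − r) for simple change and 1 − r² for ANCOVA. Power is Φ(2.802/√variance − 1.960).

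| r | Variance: post / change / ANCOVA | Power at 0.474 SD |
|---|---|---|
| 0.3 | 1 / 1.40 / 0.91 | 80 / 66 / 84% |
| 0.5 | 1 / 1.00 / 0.75 | 80 / 80 / 90% |
| 0.7 | 1 / 0.60 / 0.51 | 80 / 95 / 97% |

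For 0 < r < 1, 1 − r² is below both 1 and 2(1 − r). Against post level, 140/(1 − r²) makes 140 patients worth about 154, 187 and 275. The confidence interval is narrower by 1 − √(1 − r²), that is 5%, 13% and 29%.

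**Step 2: simulation of the tests as planned.** There were 4,000 runs per setting (Monte Carlo standard error about 0.7 points near 75%). Effects are shifts in SD units, on the raw scale for normal markers and the log scale for lognormal ones. Normal values were floored at 2% of the mean. The planned test is a t-test if Shapiro-Wilk p > 0.05 in both arms, otherwise Mann-Whitney; this check is assumed, since the SAP names none. ANCOVA uses raw or log, whichever gives the higher Shapiro-Wilk W in pooled baselines.

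| r | Post level | Percentage change | ANCOVA |
|---|---|---|---|
| 0.3 | 77-79% | 55-64% | 83% |
| 0.5 | 77-79% | 70-77% | 89-90% |
| 0.7 | 77-79% | 89-94% | 97-98% |

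(Power at 0.474 SD; ranges are over CV and distribution.)

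Converting power to patients by 140 × ((1.96 + z_ANCOVA)/(1.96 + z_pct))², ANCOVA makes 140 worth, against percentage change:

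- lognormal markers: 224-230, 194-199 and 165-167 at r = 0.3, 0.5 and 0.7;
- normal markers: 244-274, 219-231 and 199-208.

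**Step 3: disagreement.** One planned test is significant and the other not in 30-42% of trials at 0.3 SD, 22-35% at 0.474 SD, 6-24% at 0.6 SD and 0.2-8% at 0.8 SD.

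**Step 4: no true effect.** Rejection rates are 4.8-5.4% for post level, 4.6-5.9% for percentage change and 4.6-5.4% for ANCOVA. At least one planned test is significant in 8.7-10.2%.

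**Step 5: a differently built check.** This used lognormal markers, a true 20% rise, CV 50%, 6,000 runs, t-tests on each metric and ANCOVA on the log scale. Power for post / percentage change / ANCOVA was 56/42/65%, 57/58/74% and 57/81/88% at r = 0.3, 0.5 and 0.7. With no effect, either metric was significant in 7.9-9.8% over r = 0 to 0.9 and CV 30-50%.

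**The case against.** The strongest case is that this is an efficiency gain on a secondary outcome plus one missing sentence.

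- **Item 6 already ranks the metrics.** Since percentage change is the primary metric, a fair reader might carry that into item 7. The reading is reasonable, but it is not written down, and item 6 does not compare arms. One sentence would indeed remove the ambiguity, though not the loss of precision.
- **The inflated error is conditional.** This stands. It needs a rule that either result counts, and the plan states none.
- **Percentage change does use baseline.** Also true. The accurate criticism is that no regression adjustment is planned.
- **The largest gains are against the weaker metric.** Against the better planned metric the gain at 0.474 SD is 3.5-5.6 points at r = 0.3 (over post level) and 2.7-8.4 points at r = 0.7 (over percentage change). Near r = 0.5 it is larger: 9.7-12.5 points over post level. But which metric is better depends on r, which the documents do not give. ANCOVA removes the need to guess.
- **Some upper figures lean on the model.** With normal markers at CV 50%, the 2% floor lies (1 − 0.02)/0.5 = 1.96 SD below the mean, so about 2.5% of values reach it and near-zero divisors penalise percentage change. The lognormal figures (224-230 at r = 0.3) are free of this and still substantial.
- **Choosing a scale leaves discretion.** It does unless the selection rule is written down. Even then, the shape of the baseline values does not guarantee well-behaved residuals.

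**Conclusion.** The concern holds. The only named placebo comparison has two metrics per marker, no regression adjustment and no deciding rule. The planned tests are each valid, so this is a change that should be made rather than a fatal flaw.

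That ANCOVA is more precise on a matched scale follows from 1 − r² for any r between 0 and 1. The size of the gain rests on assumed r, CV, distribution and effect. It is smallest where one planned metric happens to suit the data:

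- at r = 0 there is no material gain over post level (78-79% against 77-80%);
- at 0.8 SD the gain over post level is under 1 point.

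The case is strongest for small to moderate effects, where the two planned tests often disagree.

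**What to change.** For each marker, state in the SAP that the deciding between-arm analysis is one ANCOVA of the end-of-treatment level on arm and baseline level. Report the adjusted difference, or the ratio if logged, with a 95% confidence interval.

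Fix the scale for each marker before any results by arm are seen, from baseline values pooled over both arms, and write the rule down. The rule simulated here is raw or log, whichever has the higher Shapiro-Wilk W. It chose log in 97-100% of lognormal runs and 0-2% of normal runs. Keep post-treatment level, percentage change and the planned tests as supportive.

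**Cost.** SAP wording and one regression per marker in the software already named; no new data. A documented scale decision is needed for each marker and, if logs are used, a rule for zero or below-detection values. A mismatched scale can lose power:

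- normal markers, CV 50%, r = 0.3, 0.474 SD: log-scale ANCOVA 70%, against 79% for post level;
- lognormal markers, CV 50%, r = 0.9, 0.3 SD: raw ANCOVA 95.0%, against 97.4% for percentage change; the pooled-baseline rule gives 98.2%.

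**Minimum alternative.** One sentence naming a single deciding metric for item 7. Percentage change would keep power at 55-64% at r = 0.3 and 0.474 SD; post level would keep it at 77-79% even at r = 0.7.

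**Not covered.** Neither change settles multiplicity over three markers (1 − 0.95³ = 14.3% if independent and each tested at 5%), nor does it make the placebo comparison primary. Those need separate changes.
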